##### **7.2.2.1 Pre Treatment**

- AE assessment

- Assessment of concomitant medication
- Bleeding Episode Characteristics
  - Location
  - Date/time of start of bleeding episode
  - Severity
  - Spontaneous/traumatic
- Patient Diary

#### 7.2.2.2 Treatment (Time 0 hrs)

- A  $\leq$  2 min IV push of 75 or 225  $\mu$ g/kg of LR769, depending on the dosing randomization of the patient and the 12 weeks treatment regimen he is in at the time of the bleeding episode
- Record date, time and total dose of study drug as well as number and lot of vials used for preparation in patient diary (by the patient/parent); if in hospital or hemophilia treatment center in patient records by study staff
- AE assessment
- Assessment of concomitant medication

#### 7.2.2.3 After first administration until improvement of the bleeding episode

- AE assessment (reported by the patient/parent) in the patient diary and by study staff in the patient records in hospital or hemophilia treatment center)
- Assessment of concomitant medication
- Efficacy assessments (before each new administration of the study drug to be done by the patient/parent) if home treatment and by study staff if in hospital or hemophilia treatment center in addition to patient's assessments.
- Record date, time and outcome of the assessments in patient diary (by the patient/parent); if in hospital or hemophilia treatment center in patient records by study staff in addition to patient's assessment

#### **ADMINISTRATION OF STUDY DRUG:**

##### When in 75 $\mu$ g/kg dose treatment regimen:

- If response to treatment 2 hours after first or any subsequent administration is unsatisfactory (i.e., efficacy assessment is not rated as good or excellent): a  $\leq$  2 min IV push of 75  $\mu$ g/kg of LR769 may be administered.
- If 2 hours after last administration the bleeding episode has improved (i.e., efficacy assessment is rated at least as moderate): change to treatment at 3-hour intervals for 1-2 days until good or excellent result is reached
- After 1-2 days, the interval may be increased to 4-12 hours depending on the type of bleeding episode for as long as needed

When in 225 µg/kg dose treatment regimen:

- If response to treatment 6 hours after first administration is unsatisfactory (i.e., efficacy assessment is not rated as good or excellent): a  $\leq 2$  min IV push of 75 µg/kg of LR769 may be administered. This will be repeated every 2 hours until improvement in bleeding symptoms is observed
- If response to treatment after the first or any subsequent administration is satisfactory (i.e., efficacy assessment is rated as good or excellent): change to 3 hour intervals of treatment for 1-2 days
- After 1-2 days, the interval may be increased to 4-12 hours depending on the type of bleeding episode for as long as needed
- Record date, time and total dose of study drug as well as number and lot of vials used for preparation in patient diary (by the patient/parent); if in hospital or hemophilia treatment center in patient records by study staff.

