Patients are allowed to be treated for another bleeding episode in a different anatomical location within 24 hours after initial start of treatment, provided the response to treatment of the initial bleeding episode was either "good" or "excellent" and no more treatment is needed. Definition of the response categories is provided in Section 6.8. Occurrence of a bleeding episode in the same joint/anatomical location after 24 hours of the last treatment of the initial bleeding episode when an initial "good" or "excellent" response has been achieved will be treated as a new bleeding episode. If the bleeding episode occurs within 24 hours after the last treatment of the initial bleeding episode when an initial "good" or "excellent" response has been achieved, this is regarded as a true recurrence and therefore a treatment failure. There is no restriction on the number of bleeding episodes that can be treated with LR769 for each patient in this study. The use of LR769 for prophylaxis is not permitted.

Treatment of severe bleeding episodes:

Patients with a severe bleeding episode always need to be treated in a hospital or hemophilia treatment center. However, after consultation with the study staff, the first administration of LR769 for the treatment of a severe bleeding episode may be done at home, only if this patient has already completed Phase A.

Treatment of a severe bleeding episode will be initiated as soon as possible, but certainly within 4 hours of first symptoms of the onset of the bleeding episode. Examples of severe bleeding episodes are: central nervous system (CNS) hemorrhage, throat and neck hemorrhage, acute hemorrhage in the abdomen, and gastrointestinal (GI) bleeding. Additionally, bleeding episodes associated with significant blood loss or intolerable pain such as severe episodes of joint, muscle, and soft tissue bleeding episodes leading to significant joint damage and morbidity may qualify as a severe bleeding episode. Patients with severe bleeding episodes will be treated with 75 µg/kg or 225 µg/kg, depending on randomization and the 12-week regimen in which the patient is currently participating.

During the 75 µg/kg treatment regimen, the initial 75 µg/kg dose may be followed 2 hours later with 75 µg/kg every 2 hours ± 15 minutes until improvement of the bleeding episode is observed. The dose interval can then be increased to 3 hours ± 15 minutes for 1-2 days, after

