### 3.1.2.3 Treatment of Severe Bleeding Episodes

Treatment of a severe bleeding episode will be initiated as soon as possible, but certainly within 4 hours of first symptoms of the onset of the bleeding episode. Patients with severe bleeding episodes always need to be treated in a hospital or hemophilia treatment center. However, after consultation with the study staff, the first administration of LR769 for the treatment of a severe bleeding episode may be done at home but only if this patient already completed Phase A.

Patients with severe bleeding episodes will be treated with either 75 µg/kg or 225 µg/kg, depending on the randomization and 12-week period of crossover regimen they are in.

During the 75 µg/kg treatment regimen, the initial 75 µg/kg dose may be followed 2 hours later with 75 µg/kg every 2 hours until improvement of the bleeding episode is observed. The

---

dose interval can then be increased to 3 hours for 1-2 days after which the interval may be increased to 4-12 hours depending on the type of bleeding episode for as long as needed.

During the 225 µg/kg treatment regimen, the initial 225 µg/kg treatment may be followed 6 hours later with 75 µg/kg every 2 hours until improvement of the bleeding episode is observed. The dose interval can then be increased to 3 hours for 1-2 days after which the interval may be increased to 4-12 hours depending on the type of bleeding episode for as long as needed.

In case of continued excessive bleeding of a severe bleeding episode while treated with LR769, the patient's physician will decide the best treatment in that case. This may be another bypassing agent [REDACTED] or any other hemostatic treatment effective for inhibitor patients.

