**7.2.2.4 During Continued Treatment**

- AE assessment
- Assessment of concomitant medication
- Efficacy assessments:
  - before each new administration of study drug
  - at 12 and 24 hours after start of study drug treatment (if not done as part of pre administration assessment)
  - 12 hours after last study drug administration
- Record date, time and outcome of the assessments in patient diary (by the patient/parent); if in hospital or hemophilia treatment center in patient records by study staff in addition to patient's assessment
- Administration of study drug: continue with every 3 hours administration of a  $\leq 2$  min IV push of 75 µg/kg of rhFVIIa as long as indicated by the treating physician for 1-2 days, depending on the severity and location of the bleeding episode. The duration and treatment interval may be extended (up to every 4-12 hours) based on the judgment of the treating physician.
- Record date, time and total dose of study drug as well as number and lot of vials used for preparation in patient diary (by the patient/parent) if treatment is continued at home); if still in hospital or hemophilia treatment center in patient records by study staff

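### Severe bleeds: Section 7.2.2.3 starts 3-hour dosing at a moderate rating on 75 µg/kg but at good or excellent on 225 µg/kg, while Section 3.1.2.3 and the synopsis give both regimens one trigger

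*Protocol*

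**What the plan says.** Section 7.2.2.3 (Administration of Study Drug) sets out severe-bleed dosing separately for each regimen.

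- **75 µg/kg.** A further push may be given "If response to treatment 2 hours after first or any subsequent administration is unsatisfactory (i.e., efficacy assessment is not rated as good or excellent"). The interval lengthens when "the bleeding episode has improved (i.e., efficacy assessment is rated at least as moderate): change to treatment at 3-hour intervals". That 3-hour phase is then described as running until a good or excellent result.
- **225 µg/kg.** If the 6-hour response is not good or excellent, a 75 µg/kg push may follow, and "This will be repeated every 2 hours until improvement in bleeding symptoms is observed". The interval lengthens when the response "is satisfactory (i.e., efficacy assessment is rated as good or excellent): change to 3 hour intervals of treatment".

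Section 3.1.2.3 and the synopsis describe the same step in the same terms for both regimens: 2-hourly dosing "until improvement of the bleeding episode is observed. The dose interval can then be increased to 3 hours". Neither place attaches a rating to improvement.

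The section layout also treats the regimens alike. Section 7.2.2.3 is headed "After first administration until improvement of the bleeding episode". Section 7.2.2.4 then gives one instruction, not split by regimen: "continue with every 3 hours administration of a" push of 75 µg/kg.

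Section 6.8 defines moderate as some noticeable effect, with improving signs of bleeding given as an example, while bleeding continues. Section 6.8 and the synopsis text on efficacy assessments mention a longer interval in severe bleeds only alongside good or excellent. They do not say that a lesser rating rules it out.

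**The concern.** Good or excellent is what the 3-hour phase aims for on 75 µg/kg, but it is what starts that phase on 225 µg/kg. A deliberate difference between regimens would be legitimate, but the protocol never says that it is one, and its other descriptions of the step use a single trigger.

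The practical risk lies on the 225 µg/kg regimen. A site working from Section 7.2.2.3 and a site working from Section 3.1.2.3 or the synopsis could act differently on the same moderate rating, in bleeds that Table 1 classes as capable of threatening life or limb.

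There is also a smaller analytic risk. The number of administrations and the amount of drug per bleed are summarised by regimen, with severe bleeds shown separately and combined with the rest (Sections 9.6 and 9.7). The SAP addendum adds a by-regimen count of administrations needed to reach a response under the EMA definition, for bleeds of any severity. A difference in dosing rule while a bleed is rated moderate could appear in those tables as a difference between regimens.

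**Working it through.** The plan states no figure for this step, so there is none to reproduce. The check compares the texts and then does simple interval arithmetic.

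**Step 1: what each rating triggers.**

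| Rating | 75 µg/kg, Section 7.2.2.3 | 225 µg/kg, Section 7.2.2.3 | Both regimens, Section 3.1.2.3 and synopsis |
|---|---|---|---|
| None | 2-hourly | 2-hourly from 6 h | 2-hourly |
| Moderate | Change to 3-hourly | 3-hour bullet not met; whether 2-hourly dosing ends depends on what improvement means | 3-hourly allowed if moderate counts as improvement |
| Good or excellent | 3-hourly trigger met | Change to 3-hourly | 3-hourly allowed |

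The regimens part only at moderate.

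**Step 2: the two readings of improvement on 225 µg/kg.**

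- *It includes moderate.* Two texts support this: the 75 µg/kg bullet, which spells out improved as moderate or better, and the Section 6.8 definition of moderate. Section 3.1.2.3 and the synopsis then allow 3-hour dosing at moderate. In Section 7.2.2.3 the same rating ends 2-hourly dosing without meeting the bullet that starts 3-hourly dosing.
- *It means good or excellent.* The 225 µg/kg bullets then agree with each other and with Section 3.1.2.3 for that regimen. But the word has two meanings within Section 7.2.2.3, and the matching sentences in Section 3.1.2.3 and the synopsis mean different things for each regimen.

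Neither reading makes all the sections agree with one meaning of improvement.

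**Step 3: size on 225 µg/kg.** Suppose a bleed stays at moderate for H hours after the 6-hour assessment. One site doses 2-hourly until good or excellent, and another doses 3-hourly from moderate. The difference is H/2 − H/3 = H/6 administrations of 75 µg/kg.

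| H (assumed) | 2-hourly | 3-hourly | Difference |
|---|---|---|---|
| 0 h | 0 | 0 | 0 |
| 6 h | 6/2 = 3 | 6/3 = 2 | 1 administration, 75 µg/kg |
| 12 h | 12/2 = 6 | 12/3 = 4 | 2 administrations, 2 × 75 = 150 µg/kg |

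For H = 6 the pushes before 12 hours fall at 6, 8 and 10 h in one case and at 6 and 9 h in the other.

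**Step 4: a lesser point on 75 µg/kg.** A moderate rating at 2 hours meets both the bullet allowing a further push and the bullet moving to 3-hour intervals. A push at 2 hours followed by 3-hour intervals satisfies both, but the text does not say so.

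**The case against.** The strongest reply is that this is a gap and not a contradiction. The 225 µg/kg bullet says what to do at good or excellent and is silent on moderate; it does not forbid 3-hour dosing there. The other 225 µg/kg bullet ends 2-hourly dosing at improvement, as Section 3.1.2.3 does, and Section 7.2.2.4 then continues 3-hourly. A moderate rating could follow that path without conflict.

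Section 3.1.2.3 and the synopsis are also permissive, so a site that stays 2-hourly breaches nothing there. Footnote 2 to the severe-bleed schedule in Appendix 1 leaves duration and interval to the treating physician, and severe bleeds are treated in a hospital or hemophilia center apart from a possible first dose at home. Finally, the dose difference rests on an assumed run of moderate ratings.

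Much of this stands. The divergence in site behavior depends on how improvement is read, and some variation would remain even with perfect wording. The mentions of good or excellent in Section 6.8 and the synopsis efficacy text are ambiguous, not contradictory.

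It does not remove the main point. Section 7.2.2.3 ties named ratings to named intervals, ties different ratings to the same interval in the two regimens, and gives no reason. A site cannot tell from the text which part binds it and which part is discretion.

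**Conclusion.** The concern holds. The written triggers for 3-hour dosing in severe bleeds differ by regimen in Section 7.2.2.3 and do not differ in Section 3.1.2.3 or the synopsis, and no section says that a difference is intended. The wording difference is certain; how far it would change practice is not.

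On 225 µg/kg the size is one 75 µg/kg administration per 6 hours spent at moderate after the 6-hour assessment, and zero if no time is spent there. This assumes the two readings in Step 3. The documents give neither the frequency nor the duration of moderate ratings.

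The statistical consequence is limited. Severe bleeds are expected to be a minority. They are outside the FDA primary endpoint and the sample size, and their efficacy is only described (Sections 9.2 and 9.5.1). They do count in the EMA primary endpoint, for which no hypothesis test is stated, and in the drug-use summaries. The case for correcting the text rests mainly on having one clear instruction for serious bleeds, and secondarily on those summaries. Which rating should trigger the change is a clinical matter and is not judged here.

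**What to change.** The sponsor should reconcile Section 7.2.2.3 with Section 3.1.2.3, the synopsis (both the severe-bleed treatment text and the efficacy-assessment text), Section 6.8, Section 7.2.2.4 and the severe-bleed schedule in Appendix 1. After that:

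- each rating should lead to one instruction within each regimen, including moderate on 225 µg/kg and the overlap at 2 hours on 75 µg/kg;
- the protocol should say whether any difference between regimens is intended;
- it should say where the treating physician's judgment overrides the rating-based rule.

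The choice of threshold belongs to the sponsor's clinical team.

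The cost is a wording amendment, which Section 10.2 sends for IRB/IEC approval, and a clarification letter to sites. Data collection and sample size do not change.

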**7.2.2.4 During Continued Treatment**

- AE assessment
- Assessment of concomitant medication
- Efficacy assessments:
  - before each new administration of study drug
  - at 12 and 24 hours after start of study drug treatment (if not done as part of pre administration assessment)
  - 12 hours after last study drug administration
- Record date, time and outcome of the assessments in patient diary (by the patient/parent); if in hospital or hemophilia treatment center in patient records by study staff in addition to patient's assessment
- Administration of study drug: continue with every 3 hours administration of a  $\leq 2$  min IV push of 75 µg/kg of rhFVIIa as long as indicated by the treating physician for 1-2 days, depending on the severity and location of the bleeding episode. The duration and treatment interval may be extended (up to every 4-12 hours) based on the judgment of the treating physician.
- Record date, time and total dose of study drug as well as number and lot of vials used for preparation in patient diary (by the patient/parent) if treatment is continued at home); if still in hospital or hemophilia treatment center in patient records by study staff

**7.2.3 Rescue Treatment**

In case of an insufficient effect of LR769 (e.g., insufficient effect after 24 hours for a mild/moderate bleeding episode, or continued excessive bleeding in a severe bleeding episode), the treating physician should stop treatment with LR769 and treat the patient with another therapy, such as the treatment they used prior to enrollment in this study. This may

be another bypassing agent [REDACTED] or other effective hemostatic treatment. The patient can return to treatment with LR769 for a new bleeding episode provided that at least 24 hours has passed since the other bypassing agent was given.

### **7.3 Procedures at Follow-Up Visits in Phase B**

Timepoints of visits in Phase B are all relative to the first administration of LR769 in Phase A. The visits described in Sections 7.3.1 up to and including 7.3.6 may be conducted outside the hospital/hemophilia treatment center (e.g., when travel is too burdensome for the patient) by qualified site staff or qualified health care professionals on behalf of the site staff, provided all necessary arrangements for performing the assessments are available (blood collection, etc.).

In addition to the below schedule, site staff will contact the patient's parents approximately weekly to check the following:

- To confirm patient's compliance with the study treatment
- Collect information of bleeding episodes, whether any AEs occurred, study drug availability, etc.

#### **7.3.1 3 Weeks ( $\pm 2$ days) visit**

- Check for physical signs of thromboembolic events
- AE assessment
- Assessment of concomitant medication
- Immunogenicity sample
- Patient diary check

#### **7.3.2 6 Weeks ( $\pm 5$ days) visit**

- Check for physical signs of thromboembolic events
- AE assessment
- Assessment of concomitant medication
- Immunogenicity sample
- Weight and dose adjustment if necessary
- Drug accountability
- Patient diary check and collection
- Issue new diary

---

### 7.3.3 **12 Weeks ( $\pm 5$ days) visit**

- Check for physical signs of thromboembolic events
- Safety labs (hematology, chemistry)
- Immunogenicity sample
- Weight and dose adjustment if necessary
- Crossover to alternative treatment regimen
- Vital signs
- AE assessment
- Assessment of concomitant medication
- Drug accountability
- Healthcare utilization assessments
- Patient diary check and collection
- Issue new diary

### 7.3.4 **18 Weeks ( $\pm 5$ days) visit**

- Immunogenicity sample
- AE assessment
- Assessment of concomitant medication
- Check for physical signs of thromboembolic events
- Weight and dose adjustment if necessary
- Drug accountability
- Patient diary check and collection
- Issue new diary

### 7.3.5 **24 Weeks ( $\pm 5$ days) visit**

- Immunogenicity sample
- Safety labs (hematology, chemistry)
- FVIII or FIX inhibitor sample for central lab
- Physical examination, including check for physical signs of thromboembolic events
- Weight and dose adjustment if necessary
- Vital signs
- AE assessment
- Healthcare utilization assessments
- Assessment of concomitant medication
- Drug accountability

- Patient diary check and collection
- Issue new diary

### **7.3.6 All Subsequent Visits 6 and 12 Weeks after Week 24 visit**

#### **7.3.6.1 6 Weekly ( $\pm 5$ days)**

- Immunogenicity sample
- AE assessment
- Assessment of concomitant medication
- Weight and dose adjustment if necessary
- Check for physical signs of thromboembolic events
- Drug accountability
- Patient diary check and collection
- Issue new diary

#### **7.3.6.2 12 Weekly ( $\pm 5$ days)**

- Immunogenicity sample
- Check for physical signs of thromboembolic events
- Weight and dose adjustment if necessary
- Crossover to alternative treatment regimen
- Vital signs
- AE assessment
- Healthcare utilization assessments
- Assessment of concomitant medication
- Drug accountability
- Patient diary check and collection
- Issue new diary

### **7.3.7 End of Study Visit/Early Termination Procedures**

- Immunogenicity sample
- Safety labs (hematology, chemistry)
- FVIII or FIX inhibitor sample for central lab
- Vital signs
- Physical examination, including check for physical signs of thromboembolic events
- AE assessment

- Healthcare utilization assessments
- Assessment of concomitant medication
- Drug accountability and patient diary collection

## 8 QUALITY CONTROL AND ASSURANCE

This study will be sponsored by LFB USA Inc. The sponsor will delegate specific tasks regarding the conduct of this study to a contract research organization (CRO).

Quality Control Procedures as described in LFB USA's Quality System as well as those of the CRO will be applied. A document describing which procedures will be used for which study activities at each stage of the clinical study will be part of the arrangements between the Sponsor and the CRO. This will ensure patient safety and reliability of the data.

Monitoring visits to the study sites will be conducted periodically during the study according a study specific monitoring plan to ensure that all aspects of the protocol are being followed. The study site may be audited by LFB USA's Clinical Quality Assurance auditor (or designee). The study sites will receive written notice in advance of any audit.

## 9 PLANNED STATISTICAL METHODS

### 9.1 General Considerations

This section outlines the key components of the planned statistical analyses. Detailed methodology for the statistical analyses will be documented in a Statistical Analysis Plan (SAP). The SAP may modify the plan outlined in the protocol; however, any major modifications will also be reflected in a protocol amendment. If after database lock changes are made to the SAP, these deviations will be documented in the Clinical Study Report (CSR).

All data collected in this study will be documented using summary tables and patient data listings. Continuous variables will be summarized using descriptive statistics, specifically the sample size (n), mean, median, standard deviation, minimum and maximum. Categorical variables will be summarized by frequencies and percentages.

Where applicable, analyses will be done for all patients and by age group (aged from birth to  $<6$  years and  $\geq 6$  years to  $<12$  years).

